### 11.7.4.2    **Continuous ECGs for Cardiodynamic Assessment (Part B)**

In Part B, continuous ECGs will be obtained as noted in [Table 3-5](#) using a Global Instrumentation (Manlius, NY, USA) M12R ECG continuous 12-lead digital recorder, supplied by iCardiac Technologies. The continuous 12-lead digital ECG data will be stored onto Secure Digital memory cards. ECGs to be used in the analyses will be selected by predetermined time points as defined in [Table 3-5](#), and will be read centrally by ERT. At each protocol-specified time point, 10 ECG replicates will be extracted from a 5-minute “ECG window” (typically, the last 5 minutes of the 15-minute period when the subject is maintained in a supine or semi-recumbent quiet position).

The following principles will be followed in ERT’s core laboratory:

- ECG analysts are blinded to the subject, visit, and treatment allocation
- Baseline and on-treatment ECGs for a particular subject will be over-read on the same lead and will be analyzed by the same reader.
- The primary analysis lead is lead II. If lead II is not analyzable, then the primary lead of analysis will be changed to another lead for the entire subject data set.

The ECG data collected by continuous monitoring may or may not be analyzed, or the analysis may be restricted initially to 1 or more cohorts. The decision to analyze the ECG data will be based on future development decisions for VX-121.

### **11.7.5 Spirometry (Part D Only)**

Spirometry will be performed according to the American Thoracic Society Guidelines/European Respiratory Society Guidelines.

Spirometry will be performed as outlined below:

Pre-bronchodilator spirometry is defined as spirometry testing performed for subjects who have

- withheld their short-acting bronchodilators (e.g., albuterol) or anticholinergic (e.g., ipratropium bromide [Atrovent®]) for more than 4 hours before the spirometry assessment;
- withheld their long-acting bronchodilator (e.g., salmeterol) for more than 12 hours before the spirometry assessment; and
- withheld their once-daily, long-acting bronchodilator (e.g., tiotropium bromide [Spiriva®]) for more than 24 hours before the spirometry assessment.

During the Screening Period, spirometry assessments may be performed pre- or post-bronchodilator. At all other visits, all spirometry assessments should be performed “pre-bronchodilator.” During the Treatment Period, spirometry assessments must be performed before the morning dose of study drugs at approximately the same time at each visit. Postdose spirometry assessments will be performed as noted in [Table 3-7](#).

In the event that a subject forgets to withhold bronchodilator(s), spirometry should be performed according to the following:

- If a subject’s Day 1 Visit spirometry assessment is pre-bronchodilator but, on a subsequent visit, the subject forgets to withhold bronchodilator use, a post-bronchodilator spirometry assessment will be obtained for that visit only, and the visit will not be rescheduled.
- If, on the Day 1 Visit, the subject forgets to withhold his/her dose of bronchodilator, spirometry should be performed post-bronchodilator, and all subsequent spirometric measurements (according to the schedule of assessments detailed in [Table 3-7](#)) should be performed post-bronchodilator.
- Each spirometry assessment will be recorded in the source documents as pre- or post-bronchodilator.

If more than 1 spirometry assessment is required at a visit, bronchodilators will be withheld until completion of the last scheduled spirometry assessment.

All sites will be provided with spiroometers to be used for all study assessments. Spirometry data will be transmitted to a centralized spirometry service for quality review.

### **11.7.6 Contraception and Pregnancy**

The effects of VX-121 monotherapy or in TC with TEZ and IVA on conception, pregnancy, and lactation in humans are not known. VX-121, TEZ, and IVA did not show genotoxic potential in a standard battery of in vitro (Ames test, chromosomal aberration, or micronucleus in cultured mammalian cells) and in vivo (rodent micronucleus) studies.

#### **11.7.6.1 Contraception**

Study participation requires compliance with the contraception guidelines outlined below:

- There are no contraceptive requirements for female subjects. Only females of non-childbearing potential will be enrolled ([Section 8](#)). To be considered of non-childbearing potential, the female must meet at least 1 of the following criteria:
  - o Postmenopausal: Amenorrheic for at least 12 consecutive months and a serum FSH level within the laboratory's reference range for postmenopausal females
  - o Documented hysterectomy or bilateral oophorectomy/salpingo-oophorectomy

Notes: All other females (including females with tubal ligations) are considered to be of childbearing potential and are not eligible for the study. Female subjects must have a negative serum pregnancy test at the Screening Visit in order to be eligible for the study.

- There are no contraceptive requirements for males subjects with female partners of non-childbearing potential (as defined above).
- For male subjects with female partners of childbearing potential, study participation requires the male subject to use a condom to avoid exposure of a potential embryo or fetus to study drug via the seminal fluid. In addition, study participation requires a commitment from the subject that at least 1 acceptable method of contraception will be used as a couple. Refer to Table 11-3 for more details.

**Table 11-3 Contraceptive Requirements**

Male subjects and their female (non-study) partners of childbearing potentiala	
Male subjects must use a condom with or without spermicide.a In addition, at least 1 of the following acceptable methods must be used as a couple:
 
 
• Vasectomy performed at least 6 months previously, with a documented negative postvasectomy semen analysis for sperm.
 
• Bilateral tubal occlusion (e.g., ligation) performed at least 6 months previously.
 
• Continuous use of an intrauterine device for at least 90 days before the first dose of study drug, throughout study drug treatment, and until 7 days after the last dose of study drug.
 
• Hormonal contraceptives, if successfully used for at least 60 days before the first dose of study drug, throughout study drug treatment, and until 7 days after the last dose of study drug.
 

--	--

Note: There are no contraception requirements for female subjects (who will be of non-childbearing potential) and male subjects with female partners of non-childbearing potential.

a Male subjects must use a condom to avoid exposure of the female partner (and a potential embryo or fetus) to study drug via the seminal fluid. Condom must be used during the period starting from the first dose of study drug until 7 days after the last dose of study drug.

#### **Additional notes:**

- Male subjects must not donate sperm during the period starting from the first dose of study drug until 90 days after the last dose of study drug.
- For male subjects with a female partner of childbearing potential, the couple should not plan to become pregnant during the study or within 90 days after the last dose of study drug, with the exception of couples who plan to become pregnant by artificial insemination using sperm banked by the male subject before the first dose of study drug or sperm from another source.

### **11.7.6.2      Pregnancy**

Subjects will be counseled to inform the investigator of any pregnancy that occurs during study treatment and for 90 days after the last dose of study drug.

If a subject or the female partner of a male subject becomes pregnant while participating in the study, study drug will be permanently discontinued immediately. The investigator will notify the medical monitor and Vertex GPS within 24 hours of the site's knowledge of the subject's (or partner's) pregnancy using the Pregnancy Information Collection Form.

If confirmed to be on active drug, the subject or partner will be followed until the end of the pregnancy and the infant will be followed for 1 year after the birth, provided informed consent is obtained. A separate ICF will be provided to explain these follow-up activities. Pregnancy itself does not constitute an AE.

## **12            STATISTICAL AND ANALYTICAL PLANS**

This section presents a summary of the planned safety analyses and clinical pharmacology for this study. Safety statistical analysis details will be provided in the statistical analysis plan (SAP) for this study, and clinical pharmacologic analysis details will be provided in the clinical pharmacology analysis plan (CPAP), both of which will be finalized before clinical database lock.

Final analyses will take place after all subjects have completed the study, all data have been entered in the clinical study database, and the database has been locked.

### **12.1           Sample Size and Power**

No formal sample size calculations have been performed. The number of subjects participating in each cohort of Parts A, B, and C is typical for first-in-human studies in healthy subjects and is considered sufficient to achieve the objectives of the study. Approximately 12 subjects in Part D is considered sufficient to meet the objectives of the study for this early assessment in subjects with CF.

### **12.2           Analysis Sets**

#### **12.2.1        All Subjects Set**

The All Subjects Set is defined as all subjects who were randomized or received at least 1 dose of study drug. The All Subjects Set will be used for individual subject data listings and disposition summary tables, unless otherwise specified.

#### **12.2.2        Full Analysis Set (Part D Only)**

The Full Analysis Set (FAS) will include all randomized subjects who carry the intended *CFTR* allele mutation and have received at least 1 dose of study drug in the Treatment Period. The FAS will be used for all PD and efficacy analyses in which subjects will be analyzed according to their randomized treatment group, unless otherwise specified.

#### **12.2.3        Safety Set**

The Safety Set will include all subjects who received at least 1 dose of study drug. All safety, demographics, baseline characteristics, study drug exposure, and concomitant medications will be summarized for the Safety Set.

## **12.2.4 Pharmacokinetic Set**

The PK Set will include all subjects who received at least 1 dose of study drug and for whom the primary PK data are considered sufficient and interpretable. The PK Set will be used to summarize PK plasma data.

## **12.3 Statistical Analysis**

This section presents a summary of the planned statistical analyses of safety, PK and PD for this study. Statistical analysis details will be provided in the SAP for this study, which will be finalized before clinical database lock.

### **12.3.1 General Considerations**

Only descriptive analyses will be performed; no statistical hypothesis testing will be done. Continuous variables will be summarized using the following descriptive summary statistics: the number of subjects (n), mean, SD, SE, median, minimum value, and maximum value. Categorical variables will be summarized using counts and percentages.

All individual subject data for subjects who were randomized or received at least 1 dose of study drug will be presented in individual subject data listings.

For Parts A, B, and C, the **Treatment-emergent (TE) Period** will be from the first dose date of study drug to (1) the Safety Follow-up Visit for subjects who have a Safety Follow-up Visit, or (2) 7 days after the last dose of study drug for subjects who do not have a Safety Follow-up Visit.

For Part D, the **TE Period** will be from first dose date of study drug to 28 days after the last dose date of study drug.

### **12.3.2 Background Characteristics**

#### **12.3.2.1 Subject Disposition**

The number and percentage of subjects in each disposition category (e.g., randomized, included in Safety Set, included in the FAS, completing Treatment Period, completing the Safety Follow-up Visit, and discontinuing study with a breakdown of the reasons for discontinuation) will be summarized for the All Subjects Set.

#### **12.3.2.2 Demographics and Baseline Characteristics**

Demographic and other baseline characteristics will include, but are not limited to age, sex, race, weight, height, BMI, medical history, baseline safety parameters, and baseline sweat chloride. These characteristics will be summarized for the Safety Set. No statistical tests will be done to evaluate baseline imbalances between groups.

#### **12.3.2.3 Prior and Concomitant Medications**

Medications will be coded using the World Health Organization-Drug Dictionary (WHO-DD) and presented in 2 parts:

1. Prior medication: Medication that started before the first dose of study drug, regardless of when dosing of the medication ended
2. Concomitant medication: Medication received at or after the first dose of study drug, medication that was received before initial dosing and continued after initial dosing of study drug, or medication with missing stop date

If a medication start date is on or after the date of initial dosing of the study drug, then the medication will be summarized as concomitant medication regardless of whether the medication end date is missing or not. If a medication end date is before the date of initial dosing of the study drug, then the medication will be summarized as prior medication regardless of whether the medication start date is missing or not. Note that medication that started before initial dosing of the study drug and continued after initial dosing will be summarized as prior medication and separately as concomitant medication.

Prior medications will be listed only. Concomitant medications will be summarized using preferred name.

#### **12.3.2.4 Study Drug Exposure**

Exposure to study drug in Parts C and D (i.e., duration of treatment) will be summarized for the Safety Set in terms of duration of treatment a subject received (in days), defined as the last day minus the first day of study drug plus 1.

Duration of treatment will be summarized by means of descriptive summary statistics for Parts C and D only.

Dosing administration will be presented in an individual subject data listing for all parts.

#### **12.3.3 Efficacy Analysis**

##### **12.3.3.1 Spirometry (Part D Only)**

The following parameters of  $FEV_1$  (L), forced vital capacity (FVC) (L),  $FEV_1/FVC$  (ratio), and forced expiratory flow, midexpiratory phase ( $FEF_{25\%-75\%}$ ) (L/s) will be summarized using descriptive statistics for the FAS.

In addition, a mixed-effects model for repeated measures (MMRM) with change from baseline for percent predicted forced expiratory volume in 1 second (pp $FEV_1$ ) as the dependent variable will be performed for the FAS. The model will include treatment group, visit, and treatment-by-visit interaction as fixed effects. The model will be estimated using restricted maximum likelihood. Denominator degrees of freedom for the *F* test for fixed effects will be estimated using the Kenward-Roger approximation. A compound symmetry covariance structure will be used to model the within-subject errors. Conditional on the fixed effects, missing data due to treatment or study discontinuation will be assumed to be missing at random.

Descriptive analyses of the change from baseline will be performed for VX-121 TC and placebo. Adjusted means and 2-sided 95% CIs of the treatment effect through Day 29 (averaged over Day 15 and 29), with *P* values for all within-group comparisons, will be estimated within MMRM.

#### **12.3.4 Safety Analysis**

Safety is the primary objective of this study. The overall safety profile of VX-121 will be assessed in terms of the following primary (safety) endpoints:

- Incidence of treatment-emergent adverse events (TEAEs)
- Clinical laboratory values (including coagulation studies)
- ECG outcomes

- Vital signs
- Spirometry (Part D only)

Safety analyses will be based on the Safety Set. No statistical hypothesis testing will be conducted.

For safety variables, the baseline value will be defined as the most recent non-missing measurement collected before the initial administration of study drug.

All safety data will be presented in individual subject data listings.

#### **12.3.4.1 Adverse Events**

AEs will be coded according to MedDRA. The number and percentage of subjects experiencing an AE will be summarized by the MedDRA System Organ Class (SOC) and Preferred Term (PT). AEs will be classified as pretreatment or treatment-emergent.

**Pretreatment AEs** are defined as AEs that were reported or worsened after signing the ICF up to the start of study drug dosing.

**TEAEs during the Treatment Period** are defined as any AE that worsened (either in severity or seriousness) or that was newly developed at or after the first dose date of study drug through the end of the TE Period for the Treatment Period.

Only TEAEs will be summarized in tables. All summaries of TEAEs will be presented by the severity of the AE and relationship to the study drug. Some rules that will apply to the summarization of AEs are (1) a subject with multiple occurrences of the same AE or a continuing AE will be counted only once; (2) only the maximum severity level will be presented in the severity summary; and (3) only the worst relationship level will be presented in the relationship summary.

AEs leading to death, other SAEs, dose interruption, and permanent discontinuation will be listed separately. All AEs through the Safety Follow-up Visit will be listed in an individual subject data listing, including pretreatment AEs.

#### **12.3.4.2 Clinical Laboratory Assessments**

All statistical analyses of laboratory values will be performed using SI units. Observed and change from baseline values for hematology and clinical chemistry results will be summarized at each scheduled time point. Urinalysis results will be listed only in individual subject data listings. These results will not be summarized. Clinically significant abnormal laboratory findings will be reported as AEs.

#### **12.3.4.3 Electrocardiogram**

A summary of raw values and change from baseline values will be provided at each scheduled visit for the following ECG measurements: PR, QT, QRS, and QTc intervals and heart rate. In addition, the number and percentage of subjects by maximum on-treatment value of QT/QTc intervals, categorized as  $\leq 450$  msec,  $> 450$  msec and  $\leq 480$  msec,  $> 480$  msec and  $\leq 500$  msec, and  $> 500$  msec, as well as maximum on-treatment change from baseline value of QT/QTc intervals, categorized as  $\leq 0$  msec,  $> 0$  and  $\leq 30$  msec,  $> 30$  and  $\leq 60$  msec, and  $> 60$  msec, will be provided. Clinically significant abnormal findings will be reported as AEs.

#### **12.3.4.3.1 Cardiodynamic ECG Assessment (Part B)**

[figure not shown]
If it is determined that the continuous ECG data will be analyzed, a separate analysis plan will be created for the evaluation of the continuous ECG data, including the Cardiodynamic ECG Assessment and Concentration-QTc Analysis.

#### **12.3.4.4 Vital Signs**

The following vital signs will be summarized at each scheduled time point: systolic and diastolic blood pressure (mm Hg), body temperature (°C), pulse rate (beats per minute), and respiratory rate (breaths per minute). Clinically significant abnormal findings in vital signs will be reported as AEs.

#### **12.3.4.5 Physical Examination**

PE results will be presented in individual subject data listings only. Clinically relevant results identified after screening will be reported as AEs.

### **12.3.5 Interim and IDMC Analyses**

#### **12.3.5.1 Interim Analysis**

An IA of the continuous ECG data may be performed after all subjects in Part B have completed the Safety Follow-up Visit (see [Section 12.3.4.3.1](#)). These results will be reviewed by a small unblinded Vertex team.

An IA may be performed for Parts A, B, and C after all subjects in Part C have completed the Safety Follow-up Visit.

#### **12.3.5.2 IDMC Analysis**

Not applicable

### **12.4 Clinical Pharmacology Analysis**

A detailed analysis plan that addresses the PK objectives of the study will be presented in the CPAP.

#### **12.4.1 Pharmacokinetic Analysis**

The PK parameters of VX-121, TEZ and metabolites, and IVA and metabolites will be estimated using standard noncompartmental analysis methods. The analysis of PK results for all analytes will be based on the PK Set and will be described using descriptive statistics. Further details of the PK analyses will be provided in the CPAP.

#### **12.4.2 Pharmacodynamic Analysis (Part D Only)**

The sweat chloride assessment will be performed in Part D to evaluate the effect of VX-121 on sweat chloride levels. The analysis of sweat chloride data will be based on the FAS and will be summarized using descriptive statistics.

In addition, the same MMRM model as for ppFEV1 will be used to analyze the change from baseline for sweat chloride. Adjusted means and 2-sided 95% CIs of the treatment effect through Day 29 (averaged over Day 15 and 29), with *P* values for all within-group comparisons, will be estimated within MMRM.

### **12.4.3 Pharmacokinetic/Pharmacodynamic Analyses (Part D Only)**

Correlations between sweat chloride results and PK parameters may be analyzed.

## **13 PROCEDURAL, ETHICAL, REGULATORY, AND ADMINISTRATIVE CONSIDERATIONS**

### **13.1 Adverse Event and Serious Adverse Event Documentation, Severity Grading, and Reporting**

#### **13.1.1 Adverse Events**

##### **13.1.1.1 Definition of an Adverse Event**

An AE is defined as any untoward medical occurrence in a subject during the study; the event does not necessarily have a causal relationship with the treatment. This includes any newly occurring event or worsening of a pre-existing condition (e.g., increase in its severity or frequency) after the ICF is signed.

An AE is considered serious if it meets the definition in [Section 13.1.2.1](#).

##### **13.1.1.2 Clinically Significant Assessments**

Study assessments including laboratory tests, ECGs, PEs, and vital signs will be assessed and those deemed to have clinically-significant worsening from baseline will be documented as an AE. When possible, a clinical diagnosis for the study assessment will be provided, rather than the abnormal test result alone (e.g., urinary tract infection, anemia). In the absence of a diagnosis, the abnormal study assessment itself will be listed as the AE (e.g., bacteria in urine or decreased hemoglobin).

An abnormal study assessment is considered clinically significant if the subject has 1 or more of the following:

- Concomitant signs or symptoms related to the abnormal study assessment
- Further diagnostic testing or medical/surgical intervention
- A change in the dose of study drug or discontinuation from the study

Repeat testing to determine whether the result is abnormal, in the absence of any of the above criteria, does not necessarily meet clinically significant criteria. The determination of whether the study assessment results are clinically significant will be made by the investigator.

A laboratory value that is Grade 4 will not automatically be an SAE. A Grade 4 laboratory value will be an SAE if the subject's clinical status indicates a life-threatening AE.

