i Standard 12-lead ECGs will be performed in the supine position after the subject has been at rest for at least 5 minutes. The ECG will be done before any other procedures that may affect heart rate, such as blood draws. On Days 1 and 15, ECGs will be collected before dosing and 4 hours (± 1 hour) after dosing. ECGs collected on Day 1 before dosing will be performed in triplicate.

j The predose assessment on Day 1 may be performed on the previous day (Day -1) if randomization has occurred.

k Sweat chloride will be measured in all subjects. See [Section 8.2.1](#) for information about the sweat chloride assessment for study eligibility.

l Spirometry may be performed pre- or post-bronchodilator at the Screening Visit. Spirometry will be performed pre-bronchodilator, before the morning dose of study drugs, and should be performed at approximately the same time at every other study visit. On Days 1 and 15, spirometry will also be performed pre-bronchodilator 5 hours (± 1 hour) after study drug administration.

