**7 STUDY ENDPOINTS****7.1 Primary Endpoint**

**Parts A, B, C, and D:** Safety and tolerability, based on the assessment of adverse events (AEs), laboratory test results, standard 12-lead ECGs, vital signs, and spirometry (Part D only)

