## Spirometry

Mild post-dose declines in lung function have been observed after the initial dose with another CFTR corrector not included in the current study (LUM). Although nonclinical toxicity results do not indicate a risk of lung function declines for VX-121, lung function, as assessed by spirometry, will be included in Part D to assess for post-dose declines in spirometric indices. In addition, lung function, as assessed by spirometry, will be evaluated for preliminary evidence of efficacy.

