### Sweat Chloride and Spirometry Blinding:

- During the conduct of the study, the Vertex study team will not have access to the spirometry results after the morning dose on the Day 1 Visit.
- Sites, subjects, and their parents/caregivers/companions should not be informed of their study related sweat chloride results during the Treatment Period regardless of whether the subject has prematurely discontinued treatment.
- Subjects and their parents/caregivers/companions should not be informed of their study related spirometry results during the Treatment Period regardless of whether the subject has prematurely discontinued treatment.

A limited Vertex team will be unblinded and have access to safety, PD, and efficacy data for the purpose of conducting ongoing data reviews for planning and enabling clinical development, regulatory, and chemistry, manufacturing, and controls (CMC) decisions.

Refer to [Section 12.3.5.1](#) for details regarding interim analyses (IAs).

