9.4 Safety Analysis

Safety is the primary objective of this study. The overall safety profile of VX-121 will be assessed in terms of the following primary (safety) endpoints:

- Incidence of treatment-emergent adverse events (TEAEs)
- Clinical laboratory values as specified in the CSP.
- ECG outcomes
- Vital signs (including pulse oximetry [Part D only])
- Spirometry (Part D only)

All safety analyses will be performed by treatment group/treatment sequence for each part as applicable based on the Safety Set. All safety data will be presented in the individual subject data

listings based on the All Subjects Set. No statistical hypothesis testing will be performed for safety analysis.

Table 9-1 shows the safety summaries (e.g., raw value, change from baseline, incidence, and clinical abnormalities and etc) that will be summarized for TEAEs, clinical lab values, 12-lead ECGs, vital signs, spirometry and physical examination. Details are provided in the corresponding subsections.

The incidence of TEAEs will be summarized. TEAE summaries will include the following: all TEAEs (regardless of severity or relationship to study drug), serious adverse events (SAEs), TEAE severity, TEAE relationship, and discontinuations of study drug treatment due to TEAEs.

For the non-AE safety evaluations (clinical laboratory, ECGs and vital signs), raw values, and changes from baseline will be summarized as indicated in **Table 9-1**. For example, an “X” under the raw value column (third column) means that the “Raw value” for the safety evaluation will be summarized in tables; an “X” under the “Change from Baseline” column (fourth column) means that change will be summarized in tables.

Throughout this section, “change” refers to absolute change from baseline.

Table 9-1 Summaries Planned for Safety Data

Safety Assessment	Incidence	Raw Value	Change from Baseline	Clinical Abnormalities	Threshold Analysis
TEAEs	X			NA	
Hematology/and chemistry		X	X	Listing only	X (Part D only)
Coagulation		X (Part D only)	X (Part D only)		
Urinalysis		Listing only			
12-lead ECG		X	X		X (Part D only)
Vital signs		X	X		X (Part D only)
Spirometry (Part D)		X	X	NA	
Physical Examination		Listing only		NA	

ECG: electrocardiogram; TEAEs: treatment-emergent adverse events; NA: Not applicable; X: safety assessment will be summarized in tables

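### Part D spirometry is meant to assess post-dose declines, but no planned summary measures the same-day predose-to-postdose change

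*Protocol*

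**What the plan says.** Protocol 7.1 and SAP 6.1 make spirometry part of the primary safety endpoint in Part D. Protocol 9.3.3 gives the reason: "lung function, as assessed by spirometry, will be included in Part D to assess for post-dose declines in spirometric indices". It cites mild declines after the initial dose of a different corrector. The schedule follows from this (Protocol Table 3-7, spirometry footnote): "On Days 1 and 15, spirometry will also be performed pre-bronchodilator 5 hours" after dosing.

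The analysis text is thinner:

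- Protocol 13.1.1.2 sets out when an assessment becomes an AE: "Study assessments including laboratory tests, ECGs, PEs, and vital signs will be assessed and those deemed to have clinically-significant worsening from baseline" are to be documented as AEs. Spirometry is not named. The analysis sections repeat the AE sentence for laboratory, ECG, vital-sign and physical-examination findings, but not for spirometry.
- SAP 9.4 states: "For the non-AE safety evaluations (clinical laboratory, ECGs and vital signs), raw values, and changes from baseline will be summarized". Table 9-1 does mark spirometry for raw value and change from baseline. It shows NA under clinical abnormalities and leaves the threshold cell blank. Laboratory tests, ECG and vital signs each have a Part D threshold analysis.
- SAP Appendix D holds criteria for laboratory tests, ECGs and vital signs only.
- SAP Appendix A lists a Day 1 Postdose and a Day 15 Predose and Postdose analysis visit for ECG. Spirometry shares a row with sweat chloride that has Baseline, Day 8, Day 15, Day 29 and Safety Follow-up only.

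**The concern.** The 5-hour tests on Days 1 and 15 exist to answer one question: does lung function fall in the hours after a dose? The natural statistic is the 5-hour value minus the predose value on the same day. The plan collects both values and then has no summary that subtracts one from the other.

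The Day 1 reading matters most, because 9.3.3 refers to declines after the initial dose, and it is the reading with no analysis visit. The Day 15 rule also affects the efficacy analysis, since the same window supplies the Day 15 spirometry value. At stake is whether the report can say, by treatment group, how large the post-dose change was and how many subjects fell.

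**Working it through.** **1. Where each reading goes.** Inputs: the schedule in Protocol Table 3-7 and the windows in SAP Appendix A.

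| Reading | Spirometry | ECG |
|---|---|---|
| Day 1 predose | Baseline | Baseline |
| Day 1 postdose | No window: not predose, and the Day 8 window (1, 12] excludes Day 1 | Day 1 Postdose |
| Day 15 predose | In (12, 22], loses the tie | Day 15 Predose |
| Day 15 postdose | In (12, 22], wins the tie | Day 15 Postdose |

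The two Day 15 tests fall on one day and so are equally far from the target day. Appendix A then takes the later one, the 5-hour value. SAP 9.3.1 asks for predose values in the MMRM, so the two places disagree.

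Footnote 5 of the window table allows Day 1 post-dose values into the Day 8 window, but it is attached to the laboratory and vital-signs row. Applied to spirometry it would not help. A Day 1 value is 8 − 1 = 7 days from target, whereas a visit within the ± 1 day allowance is at most 1 day away and would be chosen.

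**2. What the Day 15 change measures.** Let B be the pre-first-dose baseline, P the Day 15 predose value and Q the Day 15 5-hour value.

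- Reported change = Q − B
- Same-day change = Q − P
- Difference between them = (Q − B) − (Q − P) = P − B, the gain built up by Day 15

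Illustration with assumed values: a subject who has gained 10 points by Day 15 and then falls 10 after the dose has P − B = 10 and Q − P = −10. The reported change is 10 − 10 = 0, so neither the mean nor the minimum shows the fall.

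**3. Arm sizes.** About 12 subjects at 3:1 gives 12 × 3/4 = 9 active and 12 × 1/4 = 3 placebo, matching Protocol Figure 9-1. No sample-size calculation or SD is stated.

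**4. What a mean alone would show.** One of 9 falling by F, with the others unchanged, moves the mean by −F/9:

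- F = 5: −0.56
- F = 10: −1.11
- F = 15: −1.67
- F = 20: −2.22

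If the other eight gain 3 points (assumed), a 10-point fall leaves a mean of (8 × 3 − 10)/9 = +1.56. The planned minimum would still show −10, but only if that difference is the quantity summarised. By steps 1 and 2, it is not.

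**5. What a count would show.** Exact (Clopper-Pearson) 95% intervals:

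- 1 of 9: 11.1% (0.3% to 48.2%)
- 0 of 9: upper limit 33.6% (28.3% one-sided)
- 0 of 3 on placebo: upper limit 70.8%

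The chance of at least one faller among 9 is 1 − (1 − p)^9. For assumed true rates of 5%, 10%, 20% and 30% it is 0.37, 0.61, 0.87 and 0.96.

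**The case against.** The best defence is that Part D is a descriptive study of 12 people and nothing is hidden. Protocol 12.3.4 and SAP 9.1 put all safety data into subject listings, and the planned statistics include minimum and maximum. Reading 12 subjects' listings is quick. A categorical table adds counts with very wide intervals beside a placebo column of 3. Section 9.3.3 speaks of mild declines with another drug and says nonclinical results do not point to the risk for VX-121.

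Most of this stands, and it rules out three stronger readings that a reader might infer.

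- **That a fall is seen only inside a mean of 9.** The listings show every value, and any summarised value also appears in the minimum.
- **That spirometry is excluded from AE reporting, or that a symptom-free fall has no route to an AE.** The list in 13.1.1.2 opens with a non-exhaustive word, and 13.1.1.1 is broad: "An AE is defined as any untoward medical occurrence in a subject during the study". The significance criteria include further testing or intervention, and dose change or discontinuation, neither of which needs symptoms. Those criteria would still apply if spirometry were named, so naming it changes little.
- **That no one can see a decline while the study runs.** Protocol 10.7.1.2 says "the Vertex study team will not have access to the spirometry results after the morning dose on the Day 1 Visit", and subjects are not told their results. It does not withhold spirometry from sites, and a limited unblinded sponsor team has access to safety data.

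The defence does not answer the narrower point. The minimum helps only if the right quantity is summarised. The Day 1 5-hour value enters no by-visit summary, and the Day 15 change is taken from the wrong reference for a post-dose question. For the same-day change, the listings are all that remains.

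**Conclusion.** The concern holds in a limited form. Of the non-AE primary safety measures in Part D, spirometry is the only one both unnamed in 13.1.1.2 and without threshold criteria. More importantly, no planned summary measures the post-dose change that 9.3.3 says the test is there to assess. A reader would have to work it out by hand from the listings. The Day 15 tie rule also contradicts the predose value in SAP 9.3.1.

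The size is small. No data are lost, no hypothesis test is affected on the safety side, and individual values remain listed. The fall sizes, the 3-point gain and the faller rates above are assumptions; the documents give no spirometry threshold or variability. The conclusion also assumes that the redacted entry between SAP 9.4.6 and 9.6 does not already define a post-dose spirometry summary. Table 9-1 and Appendices A and D are readable on this point and contain none. This is an inexpensive improvement and does not put the study's conclusions at risk.

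**What to change.** 1. In SAP Appendix A, separate spirometry from sweat chloride and give it Day 1 Postdose and Day 15 Predose and Postdose analysis visits, as ECG already has. State that the Day 15 predose value feeds the MMRM, in line with SAP 9.3.1.
2. In SAP Table 9-1 and Appendix D, add a Part D descriptive summary of same-day change in ppFEV1 (5-hour value minus predose value) on Days 1 and 15, by treatment group. Include the number of subjects falling by prespecified amounts. The sponsor should set the bands before database lock. They serve tabulation only and are not management rules.
3. Optionally, name spirometry (Part D) in Protocol 13.1.1.2 as a clarification.

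The cost is a short SAP amendment and one small table from data already collected. The downside is that ordinary test variability will produce some harmless counts, and a placebo column of 3 gives limited context for them.
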